10.4 PANIC SYMPTOM SCALE

The Panic Symptom Scale English Version

item	Symptom	Absent	Intensity			Very Strong
			1	2	3	
1	dyspnea /difficulty breathing	0	1	2	3	4
2	dizziness	0	1	2	3	4
3	unsteadiness	0	1	2	3	4
4	faintness	0	1	2	3	4
5	palpitations	0	1	2	3	4
6	trembling	0	1	2	3	4
7	sweating	0	1	2	3	4
8	choking	0	1	2	3	4
9	nausea	0	1	2	3	4
10	abdominal distress	0	1	2	3	4
11	feeling unreal or detached	0	1	2	3	4
12	paresthesia/ numb or tingling feelings	0	1	2	3	4
13	hot flushes	0	1	2	3	4
14	chest pain or discomfort	0	1	2	3	4
15	anxiety, fear or apprehension	0	1	2	3	4
16	fear of dying	0	1	2	3	4
17	fear of losing control	0	1	2	3	4
18	fear of going crazy	0	1	2	3	4

Proprietary confidential information © 2019 Boehringer Ingelheim International GmbH or one or more of its affiliated companies

Proprietary confidential information © 2019 Boehringer Ingelheim International GmbH or one or more of its affiliated companies

2. LIST OF ABBREVIATIONS

Term	Definition / description
AE	Adverse Event
AESI	Adverse event of special interest
ALT	Alanine aminotransferase
AST	Aspartate aminotransferase
BI	Boehringer Ingelheim
BMI	Body mass index
BP	Blood pressure
CCK-4	Cholecystokinin tetrapeptide
CDR	Clinical Data Repository
CRF	Case report form
C-SSRS	Columbia-Suicide Severity Rating Scale
CTP	Clinical Trial Protocol
CTR	Clinical Trial Report
CV	Arithmetic coefficient of variation
DNA	Desoxyribonucleic acid
ECG	Electrocardiogram
E _{max}	Maximum effect
ENTS	Entered Set
ES	Enrolled Set
FDA	Food Drug Administration
eCRF	Electronic case report form

Term	Definition / description
gCV	geometric coefficient of variation
gMean	Geometric mean
ICH	International Conference On Harmonisation
iPD	Important protocol deviation
IQRMP	Integrated quality and risk management plan
MedDRA	Medical Dictionary For Regulatory Activities
NIMP	Non-investigational medicinal product
PD	Pharmacodynamic(s)
PDS	Pharmacodynamic parameter set
PK	Pharmacokinetic(s)
PKS	Pharmacokinetic parameter set
PSS	Panic symptom scale
R	Reference treatment
RAGe	Report appendix generator
RPM	Report Planning Meeting
SAE	Serious adverse event
SD	Standard Deviation
SOC	System Organ Class
T	Test product or treatment
$t_{1/2}$	Terminal half-life of the analyte in plasma
t_{max}	Time from dosing to maximum measured concentration of the analyte in plasma
TS	Treated set
TSAP	Trial Statistical Analysis Plan
t_z	Time of last measurable concentration of the analyte in plasma
ULN	Upper limit of normal range
VAS	Visual Analogue Scale

3. INTRODUCTION

As per ICH E9 ([1](#)), the purpose of this document is to provide a more technical and detailed elaboration of the principal features of the analysis described in the protocol, and to include detailed procedures for executing the statistical analysis of the primary and secondary variables and other data.

This TSAP assumes familiarity with the Clinical Trial Protocol (CTP), including Protocol Amendments. In particular, the TSAP is based on the planned analysis specification as written in CTP Section 7 “Statistical Methods and Determination of Sample Size”. Therefore, TSAP readers may consult the CTP for more background information on the study, e.g., on study objectives, study design and population, treatments, definition of measurements and variables, planning of sample size, randomization.

Study data (including data entered in the RAVE EDC system and external data provided by suppliers) will be stored in a Clinical Data Repository (CDR).

The statistical analyses will be performed within the validated working environment CARE, including SASTM (current Version 9.4, by SAS Institute Inc., Cary, NC, USA), and a number of SASTM-based tools (e.g., macros for the analyses of AE data or laboratory data; Report Appendix Generator system (RAGe) for compilation/formatting of the CTR appendices).

PK parameters will be calculated by means of noncompartmental analysis using Phoenix WinNonlinTM software (current version Phoenix 6.3 or higher, Certara USA Inc., Princeton, NJ, USA). Outputs for the CTR will be generated using SASTM (current Version 9.4, by SAS Institute Inc., Cary, NC, USA).

4. CHANGES IN THE PLANNED ANALYSIS OF THE STUDY

All analyses as planned in the CTP will be performed and are described in more detail in this TSAP.

The following changes compared to the protocol will be made:

No ‘Enrolled set (ES)’ will be defined in the TSAP as data of subjects discontinued before first administration of investigational trial medication will not be entered in the CDR. A correct display of the ES is therefore not possible. Due to the same reason, the ‘Entered set (ENTS)’ will be similar to the ‘Treated set (TS)’. Therefore, no ‘Entered set (ES)’ will be defined in the TSAP as well.

5. ENDPOINTS

5.1 PRIMARY ENDPOINT

The primary endpoint is a PD endpoint, as defined in Section 2.1.2 of the CTP:

- *Maximum change from baseline of Panic symptom scale (PSS) sum intensity score after CCK-4 injection.*

5.2 SECONDARY ENDPOINTS

5.2.1 Key secondary endpoints

Not applicable.

5.2.2 Secondary endpoints

Not applicable.

5.3.3 Safety and Tolerability endpoints

Safety and tolerability of BI 1358894 will be assessed based on parameters defined in Section 2.2.2.2 and Section 2.2.2.3 of the CTP:

- *Adverse events (including clinically relevant findings from the physical and neurological examinations)*
- *Safety laboratory tests*
- *12-lead ECG*
- *Continuous ECG monitoring*
- *Vital signs (blood pressure, pulse rate)*
- *Suicidality assessment (C-SSRS)*

Local tolerability of CCK-4 injections (absence or presence of "swelling", "induration", "heat", "redness", "pain", or "other findings") will be summarized with counts and percentages overall (i.e. subject-wise worst case over all injections and time points) as well as listed by injection and time point.

6. GENERAL ANALYSIS DEFINITIONS

6.1 TREATMENTS

For basic study information on treatments to be administered, assignment of treatment groups, and selection of doses, cf. Section 4 of the CTP.

Each subject is planned to be treated in two subsequent treatment periods, with one single dose of BI 1358894 or placebo in each treatment period:

- Test treatment (Treatment T):
4 x 25 mg BI 1358894 film-coated tablet in the fed state
- Reference treatment (Treatment R):
4 x placebo film-coated tablets in the fed state

Each subject is planned to be randomly allocated to one of the two treatment sequences (T-R or R-T) in a 1:1 ratio.

In addition to the two investigational treatments stated above, the following non-investigational provoking agent will be used:

- provoking agent (NIMP)
50 µg CCK-4 (cholecystokinin tetrapeptide) as i.v. bolus injection

For the selection of subjects included in the trial, subjects able and willing to participate will be exposed to the provoking agent CCK-4 at screening. After identification of CCK-4 sensitive subjects (cf. Section 3.3 of the CTP), trial subjects will be exposed to CCK-4 again within each treatment period.

For statistical analyses of AEs, the following separate analysis phases will be defined for each subject:

Table 6.1: 1 Analysis phases for statistical analysis of AEs

Study analysis phase	Label	Start	End
Screening	Screening	Date of informed consent	Date/time of first administration of BI 1358894 or placebo
On treatment	BI 1358894 or Placebo , respectively	Date/time of administration of BI 1358894 or placebo, respectively	Date/time of administration of BI 1358894 or placebo in the next treatment period, if applicable, otherwise 12:00 a.m. on day after subject's end of study participation date.

CTR Section 15, Appendix 16.1.13.1.8.2 and Appendix 16.1.13.1.8.3 AE displays will present results for the on-treatment phase only.

In CTR Section 15, AE tables (but not in Appendix 16.1.13.1.8.2 and Appendix 16.1.13.1.8.3 AE tables), the following totals will be provided in addition:

- **"Total on treatment"**, defined as the total over all on-treatment phases

CTR Appendix 16.1.13.1.8.1 displays will present results for the screening and on-treatment phases.

Additionally to the total defined above, the following total will be provided in CTR Section 16.1.13.1.8.1 AE tables:

- **"Total"**, defined as the total over all study phases (screening + on-treatment)

Statistical analyses of safety laboratory tests and vital signs will be conducted by treatment period (BI 1358894 or Placebo), with clear differentiation between baseline (cf. [Section 6.7](#)) and on-treatment measurements.

More details on the technical implementation of these analyses are provided in the ADS Plan of this TSAP.

6.2 IMPORTANT PROTOCOL DEVIATIONS

Consistency check listings (for identification of deviations from time windows) and a list of protocol deviations (e.g. deviations in drug administration, in blood sampling times, etc.) will be provided to be discussed at the Report Planning Meeting. At this meeting, it will be

decided whether a discrepant data value can be used in analyses or whether it must be corrected in the clinical database. Each protocol deviation must be assessed to determine whether it is an iPD. For definition of iPDs, and for the process of identification of these, refer to the BI reference document "Identify and Manage Important Protocol Deviations (iPD)" (2).

If any iPDs are identified, they are to be summarised into categories and will be captured in the minutes of the Report Planning Meeting via an accompanying Excel spreadsheet (3). Categories which are considered to be iPDs in this trial are defined in the integrated quality and risk management plan (IQRMP). If the data show other iPDs, the definition in the IQRMP will be supplemented accordingly by the time of the Report Planning Meeting.

iPDs will be summarized and listed. [Table 6.2: 1](#) below specifies which kind of iPDs could potentially lead to exclusion from which analysis set. The decision on exclusion of patients from analysis sets will be made at the latest at the Report Planning Meeting, after discussion of exceptional cases and implications for analyses.

Table 6.2: 1 Handling of iPDS

iPD code	iPD Category & Brief Description	Excluded from which analysis set
iPD B1	Informed consent not available/not done	All
iPD B2	Informed consent too late	None
iPD A1	Inclusion Criteria not met	PDS, PKS
iPD A2	Exclusion Criteria violated	PDS, PKS
iPD C2	Randomisation not followed	PDS, PKS
iPD C3	Non-compliance	PDS, PKS
iPD C4	Medication code broken inappropriately	PDS, PKS
iPD C5	Incorrect intake of trial medication	PDS, PKS
iPD C6	Improper washout between treatments	PDS, PKS
iPD D1	Prohibited medication use	PDS, PKS
iPD E1	Certain violations of procedures used to measure primary or secondary data	PDS, PKS
iPD E2	Certain violations of procedures (e.g. C-SSRS)	PDS, PKS
iPD F1	Certain violations of time schedule used to measure primary or secondary data	PDS, PKS
iPD G1	Certain violations of procedures used to measure primary or secondary data	PDS, PKS
iPD G2	PDs affecting safety and rights of subjects	None

6.3 SUBJECT SETS ANALYSED

As stated in [Section 4](#) of this TSAP, the ES and ENTS will not be used, as the data of these subjects are not in the CDR. The PDS and PKS will be used as defined in the CTP, Section 7.3. In this Section, the treated set was defined as:

Treated set (TS):

This subject set includes all subjects from the ENTS who were documented to have received at least one dose of study drug.

For clarification, the definition of the TS will be specified further as:

Treated set (TS):

This subject set includes all subjects that underwent screening procedures, entered the trial and were documented to have received at least one dose of *investigational* study drug.

The following Table 6.3: 1 contains the information which subject is used for which class of endpoint:

Table 6.3: 1 Subject sets analyzed

Class of endpoint	Subject set		
	TS	PDS	PKS
Primary PD endpoint		X	
Further PD endpoints		X	
Further PK endpoints			X
Safety parameters & treatment exposure	X		
Demographic/baseline endpoints	X		
Important protocol deviations	X		

6.5 POOLING OF CENTRES

This section is not applicable, because the study is performed in only one centre.

6.6 HANDLING OF MISSING DATA AND OUTLIERS

Data of screened subjects who were withdrawn from the trial prior to first administration of investigational study drug will not be reported in the CTR.

Data of subjects who drop out or withdraw from the trial will be reported in the CTR as far as their data are available. All withdrawals will be documented and the reason for withdrawal reported in the CTR.

Handling of missing PD data will be done as described in **CTP Section 7.5.3:**

For the PD endpoints PSS _____, if the period baseline value is missing in treatment period 1, it will be imputed by the corresponding value measured in treatment period 2. If the period baseline value is missing in treatment period 2, it will be imputed by the

corresponding value measured in treatment period 1. If a value is missing after CCK-4 injection, this value will not be imputed. If all four assessments after CCK-4 injection are missing for a subject, this subject is not evaluable for this endpoint in this period.

CTP Section 7.5.1: *It is not planned to impute missing values for safety parameters.*

One exception where imputation might be necessary for safety evaluation are AE dates. Missing or incomplete AE dates are imputed according to BI standards.

CTP Section 7.5.2: *PK parameters that cannot be reasonably calculated based on the available drug concentration-time data will not be imputed.*

Missing data and outliers of PK data are handled according to BI standards ([4](#)).

6.7 BASELINE, TIME WINDOWS AND CALCULATED VISITS

A separate baseline is defined for each study treatment. The baseline is the last available value before administration of the CCK-4 challenge in the respective treatment period. E.g. for PSS sum intensity score baseline is the value measured 15 minutes before administration of the CCK-4 challenge within the respective treatment period.

In addition, for vital signs displays where PTM -2:00 are considered as baseline will be provided.

Time windows are defined in Section 6.1 of the CTP. Adherence to time windows will be checked at the Report Planning Meeting.

Unscheduled measurements of laboratory data or vital signs data will be assumed to be repeat measurements of the most recent scheduled measurement (e.g. for follow-up or confirmation of a particular value). Therefore, unscheduled measurements will be assigned to the planned time point of the previous scheduled measurement.

Descriptive statistics of laboratory data will be calculated by planned time point based on the worst value of the subject at that planned time point (or assigned to that planned time point). For vital signs, descriptive statistics will be calculated by planned time point based on the last value of the subject at that planned time point (or assigned to that planned time point).

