5.2.3 Safety laboratory parameters

For the assessment of laboratory parameters, blood and urine samples will be collected by the trial site at the times indicated in the [Flow Chart](#) after the subjects have fasted for at least 10 h. For retests, at the discretion of the investigator or designee, overnight fasting is not required.

The parameters that will be determined are listed in [Tables 5.2.3: 1](#) and [5.2.3: 2](#). Reference ranges will be provided in the ISF, Section 10.

Manual differential white blood cell count or urine sediment examinations will only be performed if there is an abnormality in the automatic blood cell count or in the urinalysis, respectively.

Proprietary confidential information © 2019 Boehringer Ingelheim International GmbH or one or more of its affiliated companies

Table 5.2.3: 1

Routine laboratory tests

Functional lab group	BI test name [comment/abbreviation]
Haematology	Haematocrit Haemoglobin Red Blood Cell count/Erythrocytes Reticulocyte count White Blood Cells/Leucocytes Platelet Count/Thrombocytes (quant) Neutrophils, eosinophils, basophils, monocytes, lymphocytes
Automatic WBC differential (relative and absolute)	
Manual differential WBC (if automatic differential WBC is abnormal and clinically relevant in the opinion of the investigator), according to local procedures	Polymorphnuclear neutrophils (segs), band neutrophils (stabs), eosinophils, basophils, monocytes, lymphocytes and any abnormalities will be reported
Coagulation	Activated Partial Thromboplastin Time Prothrombin time – INR (International Normalization Ratio) Fibrinogen ESR
Enzymes	AST [Aspartate transaminase] /GOT, SGOT ALT [Alanine transaminase] /GPT, SGPT Alkaline Phosphatase Gamma-Glutamyl Transferase Glutamate Dehydrogenase (GLDH) Creatine Kinase [CK] Creatine Kinase Isoenzyme MB [CK-MB, only if CK is elevated] Lactic Dehydrogenase Lipase Amylase
Hormones	Thyroid Stimulating Hormone ¹ Free T3 - Triiodothyronine ¹ Free T4 - Thyroxine ¹
Substrates	Glucose (Plasma) Creatinine Bilirubin, Total Bilirubin, Direct Protein, Total Protein electrophoresis ¹ Albumin Albumin (Protein Electrophoresis) Alpha-1-Globulin (Protein Electrophoresis) Alpha-2-Globulin (Protein Electrophoresis) Beta-Globulin (Protein Electrophoresis) Gamma-Globulin (Protein Electrophoresis) C-Reactive Protein (Quant) Uric Acid Cholesterol, total Triglyceride Sodium Potassium Chloride Calcium Inorganic phosphate
Electrolytes	

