5.2.6.1.6 Adverse events of special interest

The term adverse events of special interest (AESI) relates to any specific AE that has been identified at the project level as being of particular concern for prospective safety monitoring and safety assessment within this trial, e.g. the potential for AEs based on knowledge from other compounds in the same class. AESIs need to be reported to the sponsor's Pharmacovigilance Department within the same timeframe that applies to SAEs, please see [Section 5.2.6.2.2](#).

The following is considered an AESI:

- Hepatic injury

A hepatic injury is defined by the following alterations of hepatic laboratory parameters:

- o An elevation of AST (aspartate transaminase) and/or ALT (alanine transaminase) ≥ 3 -fold ULN combined with an elevation of total bilirubin ≥ 2 -fold ULN measured in the same blood sample, or
- o Aminotransferase (ALT, and/or AST) elevations ≥ 10 fold ULN

These lab findings constitute a hepatic injury alert and the subjects showing these lab abnormalities need to be followed up according to the 'DILI checklist' provided in the ISF. In case of clinical symptoms of hepatic injury (icterus, unexplained encephalopathy, unexplained coagulopathy, right upper quadrant abdominal pain, etc.) without lab results (ALT, AST, total bilirubin) available, the Investigator should make sure that these parameters are analysed, if necessary in an unscheduled blood test. Should the results meet the criteria of hepatic injury alert, the procedures described in the DILI checklist should be followed.

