5.6 OTHER ASSESSMENTSS

5.6.1 Pharmacogenomic evaluation

5.6.2 CCK-4 challenge test

CCK-4 challenge tests (CCK-4 bolus iv injection of 50 µg) will be performed at the time points indicated in the [Flow Chart](#). The CCK-4 injection time, 5 h after drug administration, must be recorded. PSS assessments will be determined -15 ± 1 , 5 ± 1 , 10 ± 1 , 20 ± 1 and 30 ± 1 minutes after the injection to ensure a detailed compilation of potential changes in psychological conditions of the subjects. The time for the post CCK-4-injection blood samples must be recorded.

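### SAP 6.7 lets a laboratory value drawn after dosing be tabulated in a pre-dose row, and separately lets a 0–5 h post-dose value serve as the laboratory baseline

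*SAP*

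**What the plan says.** SAP 6.7 contains three rules that act together on laboratory data.

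- **Unscheduled values.** They "will be assumed to be repeat measurements of the most recent scheduled measurement", and so "unscheduled measurements will be assigned to the planned time point of the previous scheduled measurement". The section has no exception for a dose given between the scheduled and the unscheduled sample.
- **Value tabulated.** Laboratory descriptive statistics are "based on the worst value of the subject at that planned time point", and values assigned to that time point count as belonging to it.
- **Baseline.** "The baseline is the last available value before administration of the CCK-4 challenge in the respective treatment period". Protocol 5.6.2 fixes the interval: "The CCK-4 injection time, 5 h after drug administration, must be recorded".

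A pre-dose alternative exists for one data type only: "In addition, for vital signs displays where PTM -2:00 are considered as baseline will be provided". Laboratory data have no counterpart.

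Elsewhere, SAP 6.1 undertakes to keep baseline and on-treatment laboratory measurements distinct, refers to 6.7 for what baseline is, and leaves implementation to the ADS Plan. SAP 7.8.2 plans laboratory statistics over time, differences from baseline, and shift tables from baseline to the last on-treatment value.

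**The concern.** Treating an unscheduled value as a repeat is reasonable when nothing has happened since the scheduled sample. It is not reasonable when the investigational drug has been given in between, because the later value then measures a different condition. Unscheduled samples also tend to be drawn because something looks abnormal, and the worst-value rule makes that abnormal value the one displayed.

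The protocol foresees such samples. Retests need no overnight fast (5.2.3), raised CRP or ESR is confirmed by a second sample (3.3.4.1), and symptoms suggesting liver injury call for liver tests "if necessary in an unscheduled blood test" (5.2.6.1.6).

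At stake is whether the laboratory tables can be read as before versus after drug. An early post-dose rise could be shown as a pre-dose value. If it falls before CCK-4, it could also raise the baseline, so that later values look like an improvement.

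**Working it through.** The plan gives no figure to reproduce. The check is a timeline, followed by an illustration.

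**1. Is there a window on Day 1 with no scheduled laboratory sample?** In the copy reviewed, the Flow Chart columns cannot be matched reliably to their headings, so the schedule has to be inferred. Protocol 5.2.3 takes scheduled samples "after the subjects have fasted for at least 10 h". The Flow Chart puts breakfast at −0:30, lunch at 6:00, a voluntary snack at 8:00 and dinner at 10:00.

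- Breakfast to lunch: 6:00 − (−0:30) = 6.5 h, less than 10 h.
- Lunch to dinner: 10:00 − 6:00 = 4 h, less than 10 h.
- Earliest fasted time after dinner: 10:00 + 10 h = 20 h post-dose. The next listed time after that is 24:00.

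If the fasting rule is kept, no scheduled safety sample falls between the pre-dose sample and 24 h. That interval contains both the early drug exposure and the CCK-4 challenge at 5:00.

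**2. What do the rules do with an unscheduled laboratory value in that window?**

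| Time of draw | Planned time point assigned | Is it baseline by actual time? |
|---|---|---|
| (a) 0–5 h, no post-dose scheduled sample yet | Pre-dose | Yes, because it precedes CCK-4 |
| (b) After 5 h, no post-dose scheduled sample yet | Pre-dose | No, because it follows CCK-4 |
| (c) After a post-dose scheduled sample | That post-dose time point | No, if that sample followed CCK-4 |

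In (a) and (b) the misplaced row comes from the unscheduled-value rule. In (a) the altered baseline comes from the pre-CCK-4 definition and would arise without that rule. In (b) the value could become baseline only if baseline were picked by assigned planned time, which the SAP does not state.

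**3. Does another rule correct this?** SAP 6.1 relies on 6.7 for the meaning of baseline, so it inherits the problem. Protocol 7.3.4 assigns measurements to treatments by planned time, and an unscheduled value has only the planned time it inherits. Read literally, a Period 1 value in (a) or (b) would be assigned to screening.

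**4. Illustration.** The ALT values are assumptions, not trial data: 30 U/L pre-dose, 95 unscheduled, 60 at the next scheduled sample.

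- Drawn at 4 h: baseline as written is 95, so change = 60 − 95 = −35. With a pre-dose baseline, change = 60 − 30 = +30.
- Drawn at 8 h: baseline by actual time stays 30 and the change stays +30. The pre-dose row still shows 95, and the post-dose rise of 95 − 30 = 65 appears in no post-dose row.
- Shift in the pre-dose mean from one such subject = excess / N. With N = 20: 65/20 = 3.25 U/L. With N = 15: 65/15 = 4.33 U/L.
- The shift is proportional to the assumed excess. At N = 20, half of it gives 32.5/20 = 1.63 U/L and twice it gives 130/20 = 6.5 U/L.

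**The case against.** The strongest reply is that little is lost. Laboratory findings after first dosing that the investigator judges clinically relevant are analysed as AEs (SAP 7.8.2), and AEs are assigned by onset time, not by planned laboratory time point. A liver result meeting the protocol's criteria is an AESI with its own table, and marked laboratory abnormalities fall under other significant AEs (SAP 7.8.1). All individual values are listed (SAP 7), and the protocol has values outside the reference range highlighted in the listings (7.3.4). The last-value end of the shift table would not normally be a Day 1 sample. All of this stands, and it limits the point to summary tables.

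Two readings that a reader might infer are too strong:

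- **That post-dose abnormalities are generally counted as a pre-dose baseline.** The SAP's baseline is pre-CCK-4, not pre-dose, and a value drawn after CCK-4 does not meet that definition by actual time. The −35 versus +30 contrast comes from the baseline definition, not from the rule on unscheduled values.
- **That these values disappear from all post-dose safety reporting.** The AE, AESI and listing provisions above contradict this.

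It can also be said that SAP 6.1 should be read as limiting 6.7, that the ADS Plan may settle the matter, and that the Report Planning Meeting can decide on discrepant values. The ADS Plan is not among the documents, so this cannot be excluded. But 6.1 defers to 6.7, and the meeting's role is case by case. A stated rule that gives the wrong row should be corrected where it is stated.

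Finally, the Day 1 laboratory schedule is inferred. If a scheduled post-dose sample does come first, the value goes to a post-dose row and the misplacement does not arise.

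**Conclusion.** The point holds, within limits. Taken literally, SAP 6.7 places a post-dose laboratory value in a pre-dose row whenever no post-dose scheduled sample precedes it. Its pre-CCK-4 baseline also allows a laboratory value from the first 5 h after dosing to serve as the baseline. These are two separate defects in one section.

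The effect is confined to the by-time-point and change-from-baseline laboratory tables and, through the baseline end only, possibly the shift tables. The primary endpoint, the AE analyses and the listings are untouched. The documents give no frequency of unscheduled Day 1 samples; it is probably low. In a trial of 20, one such subject is enough to reverse the sign of his own change and move a mean by a few units under the assumed ALT values.

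The conclusion rests on a literal reading of 6.7, on the Day 1 schedule inferred from fasting and meal times, and on the ADS Plan containing no overriding rule. The change is worth making because it is specific and cheap.

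**What to change.** Amend SAP 6.7 in two places.

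1. **Unscheduled values.** State that an unscheduled value taken after drug administration in a period is never assigned to a pre-dose planned time point. It is summarised as post-dose according to its actual date and time.
2. **Laboratory baseline.** State that, for drug-safety displays, the laboratory baseline is the last value before drug administration in that period, selected by actual date and time. The pre-CCK-4 baseline for the PSS is unaffected.

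The ADS Plan should carry the same rules, so that the separation promised in SAP 6.1 follows from 6.7. The cost is SAP wording and a date/time condition in the laboratory derivation. No new data are needed.
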